### 7.5. Outcome analysis

#### Tests for Objective #1:

We will conduct log-binomial regression to estimate the effect of the two interventions on belief about medication and medication self-efficacy and needs concern. Similarly, medication adherence will be analyzed using Robust Poisson Regression.

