7.2. Baseline Characteristics

Baseline characteristics will be reported in a Table using descriptive summary statistics. These will be stratified by group assignment, and t-tests/Chi2 tests will be used to examine for inter-group differences in these characteristics.

8. Data Sources

The main data source for the trial will be the ACCESS trial RedCAP database. This contains participant group assignments and all patient reported measures from baseline, 6-month, 18-month, and 33-month surveys. It also contains individuals' unique provincial health number which will permit deterministic linkage to administrative health databases held by Alberta Health (including Alberta Precision Laboratory data, Pharmacy Information Network Data, Practitioner Claims data, Discharge Abstract Database, National Ambulatory Care Reporting System data). All PHNs were verified at the time of study enrollment to be sure that they were accurate and active. In cases where a deterministic linkage is not possible, probabilistic linkage using name, date of birth, and postal code will be used.

9. Interventions (s)

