10.1. Covariate Adjustment

Consistent with usual practice, we will only adjust the primary analysis for stratified variables (age (</>70; sex and low-income status) (48).

Assuming that randomization has worked, and we have approximately equal distribution of sociodemographic and clinic characteristics between randomization groups, we will not adjust our analyses for covariates, as this should have been dealt with through the process of randomization. If there is imbalance in important covariates between randomization groups, a sensitivity analysis will be conducted statistically adjusting for these imbalanced covariates through the modelling process.

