10.3. Handling Missing Data

Given that our primary outcome is determined using administrative data, we anticipate minimal missing data for our principal analysis. Therefore, we will use intention-to-treat principles for this analysis.

However, our secondary outcomes rely on self-reported data and therefore there may be considerable missing data points. For the analyses of these outcomes, we will undertake the following procedures for handling missing data:

We will first check the degree and patterns of missingness in the data, based on which we will consider optimal ways of handling missing data to minimise the bias potential. In the presence of missing at random (MAR) given the observed data, we will use methods such as multiple imputation or full information direct maximum likelihood to analyze the missing data.

If the MAR assumption is in doubt, then we will also conduct sensitivity analyses to assess the potential impact that missing not at random (MNAR) may have on the analytic results. Exploration of the sensitivity of conclusion to the MAR assumption may include models which allow for missingness that is not random. These models will include variables that we find to be related to missingness as well as those potentially related to the outcome (including age, sex, baseline medication adherence, comorbidities, household income).

If loss to follow-up is related to the level of the outcome being analyzed, then results obtained under the assumption of independent loss to follow-up may be biased; and in this situation, we will investigate the magnitude of this problem by using measurements taken at previous visits to predict loss to follow-up, and include variables that are determined to predict loss to follow-up in our predictive models in order to satisfy the conditions for the data to be considered MAR, with maximum likelihood techniques being used to estimate parameters. If necessary, we will also examine other approaches in consideration of how robust the results will be and whether they provide appropriately conservative estimates for the outcome analyses.

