10.5. Analysis Methods- Secondary Outcomes

Medication adherence is a binary variable and will be analyzed using log binomial regression (generalized linear models with a log link)—given the likely high prevalence of non-adherence.

EQ5D index scores are continuous and will be analyzed using linear regression.

Medication self-efficacy and concerns will be dichotomized and analyzed using logistic regression.

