10.8. Planned Subgroup Analyses

We have a priori specified particular subgroup analyses, considering the biological plausibility for subgroups. We will conduct analyses stratified by subgroup, as described in the primary and secondary outcomes sections. We will provide effects with confidence intervals for subgroups (rather than p-values), as tests of interactions for subgroups can fail to detect important effects. These will be presented in a forest plot (49,50).

The subgroups of interest include:

Gender: Men vs Women (self-reported), likely exclude gender diverse

Age: >70 years vs 65-69 years

Income group: <30,000 vs >30,000

Financial barriers: Present vs Absent

Condition type: Diabetes // CKD // ASCVD // Risk factors only

Multimorbidity: 1-2 vs 3-4 indicated conditions

Primary Care Relational Continuity: Low/Medium vs High

Specialist Involvement in the year prior to randomization: Yes vs No

On statin at baseline: Yes vs No

On ACE/ARB at baseline: Yes vs No

Living environment: supported living vs. Independent living

Baseline medication adherence: >80% PDC for all covered meds vs <80% for any covered med

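### The adherence models omit each participant's own baseline adherence, which the trial already holds; this costs precision but does not bias the result

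*Combined protocol and SAP*

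**What the plan says.** **Covariates.** Section 10.1 of the combined protocol and SAP states that "we will only adjust the primary analysis for stratified variables" (age, sex, low income). It then says that, on the assumption that randomization has worked, "we will not adjust our analyses for covariates, as this should have been dealt with through the process of randomization". It adds one safeguard: "If there is imbalance in important covariates between randomization groups, a sensitivity analysis will be conducted". Section 7.3 of the later SAP adjusts for age, sex and income status only.

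**Adherence models.** Section 10.5 of the combined document: "Medication adherence is a binary variable and will be analyzed using log binomial regression". Section 7.5 of the SAP: "medication adherence will be analyzed using Robust Poisson Regression". Neither names a baseline term.

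**Baseline adherence is held.** Section 10.8 of the combined document lists the subgroup "Baseline medication adherence: >80% PDC for all covered meds vs <80% for any covered med". Statin use and ACEi/ARB use at baseline are subgroups both there and in SAP section 7.4. Section 10.3 names variables for the missing-data models, "including age, sex, baseline medication adherence, comorbidities, household income", as related to missingness or potentially to outcome. SAP section 7.1 plans to report the baseline level of every outcome.

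**EQ-5D.** Section 8 of the combined document says the trial database holds "all patient reported measures from baseline, 6-month, 18-month, and 33-month surveys". Section 6.3 plans mixed models over time for the EQ-5D index; section 10.5 plans linear regression. Neither states the role of the baseline score.

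**The concern.** Randomization protects against systematic imbalance. It does not remove the outcome variance that a prognostic baseline variable explains. Whether a person was already being dispensed a statin or an ACEi/ARB before randomization is likely to predict coverage in the following 12 months strongly, and probably better than age, sex or income. The plan treats baseline adherence as potentially prognostic in its missing-data section, and SAP section 7.3 gives better discriminatory power as a reason to adjust, yet the effect models leave the variable out.

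At stake is the width of the interval around the adherence effects. Adherence is a named secondary objective and the first stated purpose of the interventions, and the SAP introduction describes the adherence effects as modest. Precision matters most for effects of that kind.

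**Working it through.** **1. The plan's own figure.** The only sample size stated is for the primary event rate (section 4.8 of the combined document): 14 per 100 participant-years, rate ratio 0.88, 3 years, alpha 0.05, 80% power, 1:1. The Poisson-regression formula, two-sided, gives

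N = [1.960 × √4 + 0.842 × √(2 + 2/0.88)]² / (3 × 0.14 × (ln 0.88)²) = 4667

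and 4667 × 1.01 = 4714. Both stated figures reproduce. They say nothing about adherence, for which no power is claimed.

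**2. Inputs for adherence.** From the documents: 4768 randomized (section 7.1), so 4768/2 = 2384 per factorial margin; alpha 0.05. Assumed, because the documents are silent: 60% control adherence and correlation r between baseline and follow-up adherence of 0.3 to 0.7.

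**3. Effect on precision.** Adjustment multiplies the variance by 1 − r² and the standard error by √(1 − r²). The equivalent unadjusted trial has 4768/(1 − r²) participants.

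| r | SE multiplier | Unadjusted interval wider by | Equivalent N |
|---|---|---|---|
| 0.3 | 0.954 | 5% | 5240 |
| 0.5 | 0.866 | 15% | 6357 |
| 0.6 | 0.800 | 25% | 7450 |
| 0.7 | 0.714 | 40% | 9349 |

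**4. Detectable difference at 80% power.** Unadjusted: 2.80 × √(2 × 0.6 × 0.4 / 2384) = 3.97 points. Times 0.954 this is 3.79; times 0.866 it is 3.44. Solving the two-proportion power equation directly gives 3.94, 3.76 and 3.42. With control adherence of 50% to 70%, the unadjusted value runs from 4.05 to 3.65.

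**5. Power at 60% control adherence.**

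| True gain | Unadjusted | r = 0.3 | r = 0.5 | r = 0.7 |
|---|---|---|---|---|
| 3 points | 57% | 61% | 69% | 85% |
| 4 points | 81% | 85% | 91% | 98% |
| 6 points | 99% | over 99% | over 99% | over 99% |

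**6. Simulation check.** Robust Poisson was fitted with and without binary baseline adherence, 1000 trials per scenario. With a 3- or 4-point effect, the standard-error ratio was about 0.96, 0.88 and 0.74 at r = 0.3, 0.5 and 0.7. At r = 0.5, power rose from 56% to 70% for 3 points and from 81% to 90% for 4 points. The mean log risk ratio moved by less than 0.001. Under no effect, rejection rates were 4.5% to 5.7% unadjusted and 4.6% to 5.4% adjusted.

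**7. Dependence on the denominator.** These figures use everyone randomized. If only a share f of participants is analysed for a class, detectable differences grow by 1/√f: at f = 0.5 (assumed, other inputs held), 3.97 × 1.41 = 5.6 points unadjusted and 5.6 × 0.866 = 4.9 at r = 0.5. Adherence rate and correlation would also change in such a subset.

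**The case against.** **The plan is valid as it stands.** Adjusting only for stratification factors is a prespecified, referenced choice, and the simulation shows correct type I error without the baseline term. Section 5.2 calls the secondary outcomes other than the primary's components exploratory, and no adherence power target is missed. All of this stands: the point is about efficiency.

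**Chance imbalance is already covered.** A reader might infer that imbalance in baseline users goes unexamined. The documents do not support that. Section 10.1 plans an adjusted sensitivity analysis if important covariates are imbalanced, section 7.2 compares baseline characteristics, and effects will be shown by baseline user status. These steps address imbalance but do not recover precision, because the gain comes from prognostic strength and exists under perfect balance.

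**The size is assumed.** Correlation, adherence rate and effect are all outside the documents. The one between-group adherence effect they cite, from an external trial, is 6%. Read as 6 points, unadjusted power is already 99%. This stands, and the figures are offered only as a range.

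**EQ-5D.** A reader might infer that the baseline score is left out of the EQ-5D analysis too. That is not shown. The mixed models in section 6.3 could use it as a response or a covariate. What is shown is that sections 6.3 and 10.5 name different models.

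**Objective 2 of the SAP.** The factorial ANOVA of adherence over time may include baseline as a time point. The point here concerns the regression models only.

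**Timing.** The SAP introduction reports the main adherence findings, so changing the covariates now is done with those results known. This stands and shapes the fix.

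**Conclusion.** The concern holds for the adherence regressions in both documents. They omit a baseline variable that the trial holds and uses elsewhere, and the reason given in section 10.1 addresses balance, not variance. The consequence is lost precision. A reader might infer bias or an invalid test; neither follows, since the unadjusted comparison is protected by randomization.

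The size cannot be fixed from the documents. At 60% adherence and 4768 participants, the loss is small if the correlation is 0.3 (detectable difference about 4.0 against 3.8 points) and material for 3- to 4-point effects if it is 0.5 or more (about 4.0 against 3.4 points at 0.5). It is negligible for a 6-point effect. It also depends on whether all participants or only users of a class are analysed. It would be too strong to say that the omission decides whether an effect is seen: the SAP introduction reports that modest improvements were found.

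**What to change.** **Adherence.** In SAP sections 7.3 and 7.5 (and 10.1 and 10.5 of the combined document), add to the model for each drug class the existing flag for being on that class at baseline, alongside the stratification factors. Use robust Poisson, already named in the SAP: it keeps the risk ratio and avoids the convergence problems that log-binomial can have with a strong predictor. Limit the sentence about randomization to balance.

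Baseline PDC for the class could replace the flag where the analysis population supports it. That needs a stated look-back period, because the measure in section 10.8 pools all covered drugs and gives none. It also needs a stated population: section 6.2 counts days between renewals, so a person with no dispensing may have no PDC and a value of 0 may not fit, whereas SAP section 5.3 divides by all days in the period.

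**Disclosure.** Date the change, say that the main adherence results were already known, and report the currently planned model beside the adjusted one.

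**EQ-5D.** Reconcile section 6.3 with section 10.5, and have the retained model use the baseline score.

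**Cost.** A few lines of text, at most one derived variable per class, and an openly declared post-result change.

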10.2. Distributional Assumptions and Outlying Responses

There is the potential that some participants will have had repeated hospital encounters and excessive costs. If the number of these participants is imbalanced between the randomization groups, these outliers have the potential to skew results. In order to address this potential concern, we plan to conduct a secondary analysis in which the participants in the top 1% of encounters/costs will be excluded.

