6.1. Primary outcome

Record of any of the following identified within the Discharge Abstract Database will be counted as one primary outcome. The number of composite outcomes will be used; therefore, any one individual may have multiple outcomes within the observation window.

The rates of the composite outcome will be calculated by generating the observation time, defined as the period from randomization to study completion, taking into consideration censoring for death or outmigration.

Outcome	Description	Classification Source	Codes included	Exclusions	Source
Myocardial Infarction	Acute myocardial infarction Subsequent myocardial infarction	ICD-10	I21.X I22.X	None	Quan et al. (38), Austin et al. (39)
Stroke	Central retina artery occlusion Cerebral infarction Stroke, not specified as hemorrhage or infarction Intracerebral hemorrhage Subarachnoid hemorrhage Transient cerebral ischemic attacks	ICD-10	H34.1 I63.X I64.X I61.X I60.X G45.X	None	Kokotailo and Hill (40)
Coronary Revascularization	Coronary Angioplasty Coronary endarterectomy/excision Coronary local pharmacotherapy	Canadian Classification of Health Interventions (CCI)	1.IJ.50 1.IJ.57 1.IL.35 1.IJ.76		CIHI

	Coronary Artery Bypass				
Death	Death (all-cause)	Vital Statistics			
Ambulatory Care-Sensitive Hospitalization for Diabetes	Type 1 DM with coma Type 1 DM with acidosis Type 1 DM with hypoglycaemia Type 1 DM without (mention of) complication Type 2 DM with coma Type 2 DM with acidosis Type 2 DM with hypoglycaemia Type 2 DM without (mention of) complications Other specified DM with coma Other specified DM with acidosis Other specified DM with hypoglycaemia Other specified DM without (mention of) complication Unspecified DM with coma Unspecified DM with acidosis Unspecified DM with hypoglycaemia Unspecified DM without (mention of) complication	ICD-10	E10.0^^ E10.1^^ E10.63 E10.9^^ E11.0^^ E11.1^^ E11.63 E11.9^^ E13.0^^ E13.1^^ E13.63 E13.9^^ E14.0^^ E14.1^^ E14.63 E14.9^^	None	CIHI

Outcome	Description	Classification Source	Codes included	Exclusions	Source
Ambulatory Care-Sensitive	Type 2 diabetes mellitus with ketoacidosis		E11.10 E10.10	None	Gao et al. (41)

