10.4. Analysis Methods- Primary Outcome

Consistent with an intention-to-treat analysis, we will categorize all participants by their randomization group, regardless of compliance (intention-to-treat), in our primary analysis. For those participants who are no longer actively receiving the self-management intervention or completing follow-up surveys, as permitted by CHREB, we plan to use available health administrative data until the time of death or outmigration from the province.

A Poisson model will test the main effects of the impact of the interventions on the rate of the primary outcome. This technique was chosen as individuals may experience multiple outcomes prior to the end of the study period, therefore we will account for both number of events and varying observation time within the Poisson model (by using an offset to account for losses to follow-up). The likelihood ratio test will test a negative binomial regression model within the Poisson model to examine for the presence of overdispersion. If present, negative binomial models will be used.

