10.9. Sensitivity Analyses

Sensitivity analyses will be conducted as follows:

- Excluding those who have admissions/costs in the top 1% of all participants
- Excluding participants who resided in the same household as another participant.
- We will also conduct a complete case analysis to examine the effects of the missing data, where relevant (ie. Self-reported outcomes).

11. Interaction between intervention arms

Given the factorial design of the trial, we will assess for multiplicative interaction. Because each of our two interventions was designed to address very different patient barriers to

medication adherence (financial barriers vs. Knowledge/motivation), we don't anticipate major multiplicative interaction effects.

12. Health Economic Analysis

The primary outcome will be mean total 3-year in-study health care costs for patients receiving copayment elimination (or not) and those receiving MOXIE (or not), adjusting for co-intervention received. We will include costs for hospitalization and ED visits, physician claims (specialist and primary care physician visit and procedure billing costs), prescription medications (including those subject and not subject to copayment elimination), nonphysician ambulatory costs (day medicine and day surgery clinics), and outpatient diagnostic imaging and laboratory costs. The total costs will be calculated as the sum of these costs. Alberta Health uses Canadian Institute of Health Information case-mix grouper methods to estimate hospital costs and ambulatory-case costing methods to estimate outpatient costs.

Physician claims will be based on the amount paid by Alberta Health. The cost of medications will be estimated by combining a database containing a comprehensive list of medications dispensed to all Alberta residents with a price list from Alberta Blue Cross, including dispensing fee. Diagnostic imaging and laboratory costs will be based on estimates provided by Alberta Health Services. All costs will be reported in 2021 Canadian dollars.

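### The outlier check drops the top 1% of users by encounters or cost after randomization, so it selects on the outcome and can weaken a real effect

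*Combined protocol and SAP*

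**What the plan says.** All references are to the combined protocol and SAP unless stated.

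- **Section 10.2** gives the motive: "If the number of these participants is imbalanced between the randomization groups, these outliers have the potential to skew results". The response is that "we plan to conduct a secondary analysis in which the participants in the top 1% of encounters/costs will be excluded".
- **Section 10.9** lists the same step as a sensitivity analysis: "Excluding those who have admissions/costs in the top 1% of all participants". This wording implies a single pooled cut, not one within each arm.
- **Section 6.1** makes the primary outcome a recurrent count: "The number of composite outcomes will be used; therefore, any one individual may have multiple outcomes within the observation window".
- **Section 12** makes mean total in-study cost over three years the primary outcome of the economic analysis.
- **Section 10.4** keeps everyone in the main analysis: "we will categorize all participants by their randomization group, regardless of compliance (intention-to-treat), in our primary analysis". It tests the counts for overdispersion: "If present, negative binomial models will be used".

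Neither 10.2 nor 10.9 says whether encounters means all causes or only outcome-related ones, whether encounters and costs are cut separately or jointly, or how a changed result would be read. Neither gives a time window. The wording of 10.2 and the in-study costs of section 12 point to follow-up, and I read it so.

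**The concern.** A participant is dropped for what happened after randomization. For the cost analysis, the variable that decides exclusion is the outcome itself. For the primary outcome it is a close relative, because most component events are hospital admissions.

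Section 10.2 treats an imbalance in heavy users as a nuisance. Chance can produce such an imbalance, but so can an intervention that prevents repeat admissions. With a pooled cut, an effective intervention loses fewer people to the exclusion than its control, and the high counts that are removed come mostly from control.

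At stake is the reading of a robustness check. If a true benefit shrinks after trimming, a reader may call the main result fragile when the rule itself caused part of the shrinkage. The plan gives no warning of this.

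**Working it through.** **1. The plan's own figure.** Section 4.8 gives 14 events per 100 person-years, a 12% relative reduction, 3 years, 80% power and 1:1 allocation. I assume a two-sided 5% test. The Poisson-regression formula is

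N = [z(0.975)·√4 + z(0.80)·√(2 + 2/0.88)]² / (3 × 0.14 × ln(0.88)²) = 4667,

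and 4667 × 1.01 = 4714. Both match section 4.8, so these inputs carry over.

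**2. Spread of the counts.** The control mean over 3 years is 3 × 0.14 = 0.42. Section 4.8 also gives a 26% risk of any event. For a negative binomial count, (1 + 0.42/k)^(−k) = 1 − 0.26 = 0.74, which gives k = 0.476. The negative binomial shape is my assumption. The 26% figure does not list revascularization and the rate does, so k is approximate and I vary it from 0.2 to 2.

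**3. Trim under the planning assumption.** With N = 4714 and a rate ratio of 0.88 for everyone, remove the pooled top 1% by event count, splitting ties at the cut at random.

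- The cut falls at 4 events. About 27 control and 20 intervention participants go (47, or 1% of 4714), with about 13% of all events.
- The remaining rates are 12.2 and 11.0 per 100 person-years. From unrounded values the rate ratio is 0.904.
- Share of the log effect lost: 1 − ln(0.904)/ln(0.88) = 1 − 0.101/0.128 = 0.21.
- Tie handling: 0.898 if nobody tied at the cut is dropped, 0.909 if all are.
- Dispersion: 0.916 at k = 0.2 (31% lost) and 0.894 at k = 2 (13% lost).
- With a true rate ratio of 1.00, the trimmed value is 1.00.

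**4. Other assumptions (k = 0.476, pooled 1% cut).** Capped means counts set to the cut value with everyone kept.

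| Assumed effect | All data | Trimmed | Capped |
|---|---|---|---|
| 0.88 for everyone | 0.880 | 0.904 | 0.887 |
| 0.7 in the frailest 10%, 1.0 elsewhere | 0.87 | 0.94 | 0.88 |
| 1.0 in the frailest 10%, 0.78 elsewhere | 0.879 | 0.867 | 0.876 |

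- **Broader cut.** Take 0.88 for everyone, but cut on total encounters. Let the other encounters be unaffected by treatment, share the same frailty, and number 1 to 3 times the primary events. The trimmed ratio is then about 0.89.
- **Separate heavy-user group.** Let 5% of participants be heavy users and hold the overall ratio at 0.88. Trimming is neutral when the heavy users' ratio is about 0.94. It moves away from 1, to 0.849, when that ratio is 1.00.
- **Costs.** With lognormal costs and an assumed log-SD of 1.0 to 1.6, a true mean ratio of 0.88 becomes 0.90 to 0.91.

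**The case against.** The strongest reply is that this is an ordinary leverage check. A few extreme users can fall unevenly between arms by chance, and it is fair to ask whether they drive the result. The analysis is labelled secondary or sensitivity, and nothing lets it override the main result. The main analysis keeps every participant and moves to a negative binomial model if needed. Section 12 uses the bootstrap and a gamma model for skewed costs. All of this stands, and it keeps the point minor. It does not make the rule sound, because deletion cannot tell chance imbalance from imbalance caused by treatment. Capping limits leverage without removing anyone.

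Three stronger readings are tempting, and the documents do not support them.

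- **That the exclusion always pulls toward no effect.** It does so under the single 12% reduction of section 4.8. The documents do not say how heavy users respond, and if they benefit little the shift vanishes or reverses.
- **That admissions are the primary outcome.** Section 6.1 counts specified events, including deaths from vital statistics. The encounters in 10.2 and admissions in 10.9 are not limited to those events. Only for cost is the selection exactly on the outcome.
- **That the trial's main conclusion is at risk.** The primary estimate, sample size and alpha are unaffected, and in the event-count model with no effect trimming leaves the ratio at 1.00.

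The separate SAP's Introduction says that main findings have been reported. That limits what can be changed, but the written rule still needs the caution.

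**Conclusion.** The concern holds as a minor point about interpretation. Sections 10.2 and 10.9 select participants on post-randomization data that are the outcome (cost) or close to it (admissions), so the trimmed comparison is not a randomized one. Under the planning assumptions, trimming on the event count, 0.88 becomes about 0.90 (0.89 to 0.92 for k from 0.2 to 2), and about a fifth of the log effect is lost at the calibrated k. The shift is larger if benefit is confined to the frailest, and smaller if the cut is on broader utilization. The size rests on assumed count and cost distributions, a pooled cut, and follow-up as the window for encounters and costs. The direction rests on heavy users benefiting about as much as others, or more.

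**What to change.** In sections 10.2 and 10.9, replace the exclusion with an analysis that keeps all randomized participants and caps counts and costs at the pooled 99th percentile, reported beside the main estimate. Define encounters, the time window, and whether counts and costs are capped separately.

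If the exclusion analysis is kept as well, report the number excluded by arm. State that some attenuation is expected from the rule and is not by itself evidence against an effect.

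The cost is a short change in two sections and no new data. Capping has a small price of its own: it still shifts the rate ratio by about 0.01 to 0.02 where trimming attenuates. For results already reported, the same caution can go beside the trimmed estimate, and the capped version can be used in the further sub-analyses that section 4.12 foresees.
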